## 8. PLANS FOR PUBLICATION

Neither the complete nor any part of the results of the study carried out under this protocol, nor any of the information provided by the sponsor for the purposes of performing the study, will be published or passed on to any third party without the consent of the study sponsor. Any investigator involved with this study will be obligated to provide the sponsor with complete test results and all data derived from the study.

**10. APPENDIX****10.1 Appendix A: Reader Study Data Collection Form**

Subject ID: \_\_\_\_\_

Reader: \_\_\_\_\_

Date: \_\_\_\_\_

**Overall Assessment:**

Is there a fracture?

If yes, which bone?

Overall confidence in presence of a fracture (0-100) \_\_\_\_\_ %

Please indicate your overall confidence for each of the items below.

	Very Poor	Poor	Fair	Good	Excellent
Articular Surfaces					
Cortical Surfaces of Bones					
Joint Spaces					
Soft Tissue Structures					
Subarticular Structures

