#### **4.4 Reader Study**

Upon completion of all study image data collection, a reader study will be performed with three MSK fellowship trained radiologists. All images will be reconstructed with our fast-reconstruction algorithm and presented on 3MP viewing monitors with PACS viewing software with conventional zoom/pan/window and level tools. The readers will not be blinded whether the images are from Tomo-E.

Each radiologist will be randomly presented with either the patient's diagnostic radiographs or tomosynthesis study in a random order. They will be asked to review the scan for the presence of a fracture, and comment on location (specific bone) and fracture type. They will be asked their confidence rating on a scale of 0 to 100%.

A washout period of four weeks will be utilized so that the radiologists will have "forgotten" their initial interpretations. At this timepoint, the other modality for each patient will be randomly presented. Diagnostic accuracy will be defined by the presence of a fracture as defined by the clinical diagnosis by the attending orthopedic surgeon at 2 months post imaging during the patients' routine clinical care, such as cast placement, surgery, or follow-up imaging. Sensitivity and specificity to the presence of fractures will be estimated and evaluated between the modalities.

The order that imaging modalities will be presented will be randomly assigned using a computational software in collaboration with the study biostatistician. This randomization schedule will be created prior to the beginning of the reader study and will not be shared with any of the readers.

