#### **4.5 Variables of Interest**

Primary Variables of Interest:

- Presence of fracture based on imaging (T/F)
- Confidence in interpretation of image set (0 to 100%)

Secondary Variables of Interest

- Reader confidence in articular surface evaluation (1-5)
- Reader confidence in Cortical surface evaluation (1-5)
- Reader confidence in Joint Space evaluation (1-5)

- Reader confidence in Soft tissue Structures evaluation (1-5)
- Reader confidence in Subarticular structure evaluation (1-5)

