### 5.3 Statistical Methods

A total of 50 participants will be recruited for this study. Three radiologists will be recruited to conduct the reader study.

We will perform sensitivity, specificity and area under the curve (AUC) analysis of the imaging modalities based on radiologist reader studies. We will also perform reader confidence studies in evaluation of imaging characteristics relevant to wrist pain imaging.

The primary outcome of interest is the sensitivity of Tomo-E is defined as the ability of readers (radiologists) to detect wrist fractures in patients. This will be determined by performing a reader study with radiologists. Using these results, we can determine the mean confidence score of radiologist readers using the new device as compared to the competing modality. We will also test the primary null hypothesis that the difference between the two mean confidence scores is zero in the target population.

For the confidence study, the average confidence scores and the corresponding standard deviations will be reported. Furthermore, to test whether the mean confidence score is larger than zero, a linear mixed-effects model will be used to analyze data, where the outcome variable is the confidence scores collected in this study and only a grand mean parameter is in the independent list. Additionally, a random intercept is used in the model to account for the correlation among readers when reading the images from the same patient. The Wald's test based on model fit will be used to test whether the grand mean parameter is larger zero. When the p-value from this test is less than 0.05, it will be concluded that there exists significant evidence that readers have more confidence with the Tomo-E modality compared to the other modality. The estimated mean confidence score is given by the grand mean parameter and its 95% confidence interval will be reported. We anticipate that it would be meaningful to detect a mean confidence score of greater than 1 between the modalities.

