For the primary and secondary objective, we will estimate the sensitivity and specificity for a pre-specified cutoff of review scores to detect wrist fracture. Generalized estimating equation will be used to produce such estimates, where diagnosis outcomes from readers are treated as clustered data and a compound symmetry working covariance matrix is used. Normal distributions will be used to construct 95% confidence intervals. Bootstrap method may be used when the normality assumption is of concern. For the AUC analysis, the same estimating procedures will be used to obtain the sensitivity and specificity when varying cutoff scores then the AUC will be calculated using the trapezoidal rule. The confidence of the AUC will be obtained from bootstrap method.

For the confidence study, we expect no missing data or drop out. For any missed data during the reader study, we will question the reader to collect the data. The only primary hypothesis test is whether the mean confidence score is zero with a significance level of 0.05. There is no need to adjust multiple tests. All hypothesis tests that are observed to be not statistically significant will be reported as being inconclusive.

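### The reader form's 0-100 item (fracture present) is not the primary 0-100 variable of Section 4.5 (confidence in the interpretation), and Section 5.3 does not say which score its only primary test uses

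*Combined protocol and SAP*

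**What the plan says.** - **Section 4.5** lists two primary variables: "Presence of fracture based on imaging (T/F" and "Confidence in interpretation of image set (0 to 100". The five structure-specific confidence items, scored 1-5, are listed as secondary.
- **Section 4.4** does not say what the rating refers to: "They will be asked their confidence rating on a scale of 0 to 100".
- **Appendix A**, the form readers complete, asks whether there is a fracture and which bone, then "Overall confidence in presence of a fracture (0-100". No meaning is given for 0 or 100. The only other ratings are the five structure items on a five-step scale.
- **Section 5.3** declares one primary test: "The only primary hypothesis test is whether the mean confidence score is zero with a significance level of 0.05". In its mixed model, "the outcome variable is the confidence scores collected in this study". If p is below 0.05, "it will be concluded that there exists significant evidence that readers have more confidence with the Tomo-E modality compared to the other modality". The relevant size is given without a scale: "We anticipate that it would be meaningful to detect a mean confidence score of greater than 1 between the modalities".
- **Section 5.3** also ties sensitivity and specificity to a cutoff of review scores that it calls pre-specified, without a value. It builds the AUC by varying the cutoff on those scores.

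**The concern.** Confidence that a fracture is present runs from no to yes, with uncertainty in the middle. Confidence in the interpretation runs from unsure to sure, whatever the answer. The first suits an AUC but not a test of whether readers are more confident. The second suits the confidence test but, taken alone, cannot rank patients by likelihood of fracture. The plan collects one unanchored item and needs it for both purposes.

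At stake is the conclusion of the only primary test. A real gain in confidence could appear as no change or a fall, and a rise in positive calls could be reported as greater confidence. Readers may also use the scale differently from one another, which the analysis could not detect from the score alone.

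**Working it through.** **No planned figure to reproduce.** The plan gives no expected mean, standard deviation or power for the confidence test; the 70% power in Section 5.4 concerns sensitivity. The core of the point is a comparison of wording, and the arithmetic shows what follows from it.

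**Inputs.** From Section 5.4: radiograph sensitivity 65%, Tomo-E sensitivity 80%, prevalence 33%. Assumed: specificity, the scores readers give, and the reader model in step 5.

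**1. One reader, two items.** A reader 95% sure that there is no fracture enters about 95 under the Section 4.5 wording and about 5 under the literal form wording.

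**2. Raw mean of the literal form score.** Let a yes call score 50 + k and a no call 50 − k. The share of yes calls is q = prev × sens + (1 − prev) × (1 − spec), and the mean is 50 + k(2q − 1).

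*Same calls, more certainty.* Sensitivity 65%, specificity 80%, prevalence 33%: q = 0.33 × 0.65 + 0.67 × 0.20 = 0.3485, so 2q − 1 = −0.303.
- Scores 80/20 (k = 30): 50 − 30 × 0.303 = 40.9.
- Scores 95/5 (k = 45): 50 − 45 × 0.303 = 36.4.

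The mean falls by 4.5 points while distance from 50 rises from 30 to 45. At prevalence 20%, 50% and 67% the change is −6.3, −2.25 and +0.045. Whenever fewer than half the calls are positive, greater certainty in the same calls lowers the mean.

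*Better accuracy, same certainty.* Scores 90/10 (k = 40), sensitivity 65% to 80%, prevalence 33%; the change is 80 × (change in q).

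| Specificity, radiograph to Tomo-E | q | Change in mean |
|---|---|---|
| 80% to 80% | 0.3485 to 0.3980 | +3.96 |
| 80% to 85% | 0.3485 to 0.3645 | +1.28 |
| 80% to 90% | 0.3485 to 0.3310 | −1.40 |

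Distance from 50 is 40 throughout. The mean does not move when specificity rises by 0.33 × 0.15 / 0.67 = 7.4 points. So the raw mean can rise with no change in certainty, and can fall when both accuracy measures improve.

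**3. The other reading.** Suppose readers enter confidence in their answer. Sure negatives and sure positives then both score high. For calibrated readers with an ROC curve through 80% sensitivity and 80% specificity (binormal model, separation 0.842 + 0.842 = 1.683), the AUC is 0.88 for the signed score and 0.33 for the unsigned one. Combining the unsigned score with the yes/no call on the form restores the sign.

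**4. The difference of 1.** On 0-100 it is 1/100 = 1% of the range. On 1-5 it is 1/4 = 25%. Section 4.5 points to the first scale; the size of the difference and objective 2.2.2 fit the second.

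**5. The cutoff.** In the same model at 33% prevalence (separation 1.227 for radiographs, 1.683 for Tomo-E), score cutoffs of 30, 50 and 70 give sensitivity 76.6% to 82.2%, 51.4% to 66.3% and 25.6% to 46.7%: gains of 5.6, 14.9 and 21.1 points. No single cutoff in this model gives 65% and 80% together. It shows only that the cutoff matters if a score cutoff is used.

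**The case against.** The form has no anchors. The item follows directly after the fracture question, and Sections 4.4 and 4.5 speak of a confidence rating and of confidence in the interpretation. A reader who answers no might well enter 95 to mean sure. This stands: the literal reading is likely, because the form is what readers complete, but it is not certain. A reader might infer that the primary test certainly measures positive calls rather than confidence; the documents do not support that.

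Much can also be recovered. The yes/no call is recorded beside the score, so an unsigned score can be signed, and distance from 50 can be computed from a signed one. This holds if all readers use the scale in the same way, which the unanchored form does not secure. The choice would also be made after the reads.

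Other stronger inferences fail:
- **That the plan designates no primary confidence score.** Section 4.5 labels the 0-100 score primary and the 1-5 items secondary. What is missing is the link to 5.3, and the form does not collect that score as worded.
- **That sensitivity is undefined without a cutoff.** Section 4.5 lists the T/F call as primary, 5.1 speaks of readers detecting fractures, and 5.3 models readers' diagnosis outcomes. These point to the T/F call, so the missing value is mostly a missing detail.
- **That the raw test has no power.** In simulations with 50 patients and 3 readers it was significant in about 5% of trials, against 93-96% for distance from 50. That contrast holds only for perfectly calibrated readers, whose mean score equals prevalence (33.0 for both modalities) by construction. Nothing in the documents supports that assumption.
- **That the test passes trivially because all scores are positive.** Section 5.3 states its null hypothesis as a zero difference between the two modality means, so a difference is intended, although the model sentence does not say so.

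This is a 50-patient pilot, but it still sets a primary test at 0.05 with a fixed conclusion.

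**Conclusion.** The concern holds, and the text must be corrected before the reads. Section 4.5 and the form describe different quantities under one 0-100 scale, 5.3 does not say which score it tests, and one unanchored item cannot serve both a raw-mean confidence test and the AUC. That rests on wording alone.

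The size of the consequence depends on assumptions. If the form is taken literally and used raw, the illustrated changes in the mean at 33% prevalence run from −4.5 to +4.0 points. Their sign does not track confidence, and each is larger in absolute value than the difference of 1, should that be meant on the 0-100 scale. If readers score confidence in their answer, the confidence test is sound and the AUC is the part that fails, unless the call is used with the score. The cutoff is a clarification, not a further error of the same weight.

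**What to change.** Before reading starts:

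1. Anchor the form item (0 = certainly no fracture, 100 = certainly fracture) and use it for the AUC.
2. For the confidence test, choose one of two routes: add one form line worded as in Section 4.5, which keeps the declared primary variable, or derive certainty as the distance of the anchored score from 50. Align 4.4, 4.5, 5.3 and the form with the choice.
3. In 5.3, name the tested outcome as the within-reader, within-patient Tomo-E minus radiograph difference in that score, and state the scale of the difference of 1, restating its size if needed.
4. As a clarification, state that sensitivity and specificity use the T/F call, or print the score cutoff.

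Cost: wording, plus one extra form entry per reading on the first route; no extra patients, readers or readings. On the second route the derived score measures certainty, not correctness, so it must be reported beside sensitivity, specificity and AUC. Section 5.4 plans power for sensitivity only, so neither route gives the confidence test a planned power.
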